9.3.3. Laboratory Tests

All laboratory data will be listed and only central laboratory data will be analyzed. Laboratory data and change from baseline (haematology, biochemistry or urinalysis) will be summarized with descriptive statistics (continuous variables) or as distributions (categorical variables) by visit up to week 96 except for pregnancy test parameter. For urinalysis parameter, a shift table from baseline up to Week 96 will be presented.

The categories for out of reference range will be Low, Normal and High for Hematology, Biochemistry and Urinalysis, and Normal and Abnormal for Urinalysis (Qualitative Value). For these categories, a shift table from baseline to each visit up to Week 96 will be presented.

Laboratory test values will be considered potentially clinical significant (PCS) if they meet either the low or high PCSV criteria listed in section 8.4.3.3. A shift table describing the number and percentage of subjects shifting from non PCSV at baseline to PCSV at post-baseline will be performed any time during treatment period.

The percentages will be calculated from the number of subjects with available baseline values and any time post-baseline value

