d. Physical examination:

1. A full physical examination will consist of an assessment of major body parts and systems: abdominal, cardiovascular, general appearance, head, eyes, ears/nose/throat, lymph nodes, musculoskeletal, neck, neurological, dermatological, respiratory, and other.
2. Routine physical examination will include abdominal, cardiovascular, general appearance, respiratory, neurological, and other.

e. A 12-lead ECG will be performed after the subject has rested for at least 5 minutes in a supine position. The ECG must include the following measurements: R wave to R wave (RR) interval, heart rate, QRS, QT, QTcB, and QTcF. The Investigator will perform an overall evaluation of the ECG for safety purposes and the recording will be reported as 'normal', 'abnormal clinically significant (CS)', or 'abnormal not clinically significant (NCS)'. Abnormalities of clinical significance will be reported as AEs.

f. Events are time to death, tracheostomy, or permanent assisted mechanical ventilation (> 23 hours/day).

g. To include: Red blood cell count, hemoglobin, hematocrit value, white blood cell count including differential, and platelet count

- h. To include: albumin, total protein, aspartate aminotransferase (AST), alanine aminotransferase (ALT), lactate dehydrogenase (LDH), alkaline phosphatase (ALP), total bilirubin, direct bilirubin, CK, total cholesterol, triglycerides, BUN, bicarbonate, serum glucose, serum creatinine level, uric acid, sodium (Na), potassium (K), chloride, and calcium (Ca). Note: albumin will be included in the chemistry profile for Weeks 24, 48, 72 and 96 only. The Day 1/screening assessment will not include albumin as it was not collected as part of Study MT-1186-A01 chemistry profile.
  - i. To include protein, glucose, occult blood, urobilinogen, white blood cells, and bilirubin.
  - j. Subjects will receive oral edaravone at a dose of 105 mg administered once daily for 10 days out of a 14-day period, followed by a 14-day drug- free period for 96 weeks of treatment or until the drug is commercially available in that country. The dose of edaravone should be taken following an overnight fast and at least 1 to 2 hours before the morning meal.
  - k. Drug compliance should be assessed on a per cycle basis by site staff via phone calls or during the in-clinic visits.

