### **9.4 Exclusion Criteria**

Subjects who meet any of the following criteria will be excluded from the study:

1. Subjects who are able to bear children and who do not have a negative pregnancy test, women who are nursing or who do not agree to use a highly effective form of contraception from Visit 1 until 3 months after the last dose of study medication. Refer to Appendix 2 for additional contraceptive information.
2. Subjects who have a significant risk of suicide. Subjects with any suicidal behavior or suicidal ideation of type 4 (active suicidal ideation with some intent to act, without a specific plan) or type 5 (active suicidal ideation with specific plan and intent) based on the C-SSRS at Visit 1.
3. Subjects who are not eligible to continue in the study, as judged by the Investigator.
4. Subjects who are unable to take their medications orally or through a PEG/RIG tube.

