#### **10.1.3 Safety Follow-up Period/End of Study/Early Termination**

A safety follow-up period (e.g., Visit 9, Week 96 [ $\pm 7$  days]) will be conducted for subjects who complete the open-label treatment period, per the Schedule of Assessments (Table 1).

For subjects who terminate early from the study, assessments should be performed per the Schedule of Assessments (Table 1) within 7 days of study discontinuation.

Any unresolved AE or SAE will be followed up according to Section 15.8.

In the event that a subject elects not to return to the clinical site for the ET Visit, the Investigator must make every effort to contact the subject to review all AEs. In the event that a subject drops out of the study at any time, the reason for discontinuation must be fully documented in the source documents and the eCRF. The Investigator site personnel will document the AEs and any other assessments in the source documents and will make every effort to complete all required ET assessments.

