7. STATISTICAL CONSIDERATIONS

7.1. Descriptive Statistics

All data from all subjects enrolled into the study will be included in patient data listings. The listings will be sorted by center and subject number (and by visit, if applicable).

Continuous data will be summarized descriptively using the number in the analysis population set (N), the number of observations (n), mean, standard deviation (SD), median, minimum and maximum. Categorical data will be summarized using frequency counts and percentages. The denominator for the percentages will be the total number of subjects in the treatment group and analysis population being presented, unless otherwise specified. For visit-specific data, the number of subjects with non-missing observations at the visit in question will be used as the denominator for percent calculations. Unknown, Not Done, Not Applicable and other classifications of missing data will not be considered.

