8. DATA CONVENTIONS

8.1. Baseline Definition

In general, the data at Week 48 in Study MT-1186-A01 (same time as A03 Visit 1/Day 1) will be used as the baseline for statistical analysis in this study. The analyses involving calculation of change from baseline will be based on the absolute changes from baseline (not percentage), unless stated otherwise.

The time (days) to death, tracheostomy, or permanent assisted mechanical ventilation (≥ 23 hours/day) will be analyzed using the time from first study drug administration in the MT-1186-A01 study.

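### The PCSV shift percentage in SAP 9.3.3 keeps subjects already PCSV at baseline in its denominator, so it can understate the incidence of new laboratory abnormalities

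*SAP*

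**What the plan says.** SAP 9.3.3 defines the table as "A shift table describing the number and percentage of subjects shifting from non PCSV at baseline to PCSV at post-baseline", and adds that this "will be performed any time during treatment period". The closing sentence of the section fixes the denominator: "The percentages will be calculated from the number of subjects with available baseline values and any time post-baseline value". It requires a pair of values. It does not require the baseline value to be non-PCSV.

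The general rule in SAP 7.1 adds no such restriction. It reads "The denominator for the percentages will be the total number of subjects in the treatment group and analysis population being presented, unless otherwise specified", and for data by visit it uses the subjects with an observation at that visit.

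Three other places determine who can already be PCSV at baseline:

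- SAP 8.1 sets the reference point: "the data at Week 48 in Study MT-1186-A01 (same time as A03 Visit 1/Day 1) will be used as the baseline". Baseline therefore comes at the end of the parent study, in which the same dose was given (Protocol 8.2.2).
- Protocol 9.4 lists four exclusion criteria, none with a laboratory threshold. The nearest is a matter of judgement: "Subjects who are not eligible to continue in the study, as judged by the Investigator".
- SAP 8.4.3.3 lists the PCSV criteria. Nearly all are cut-offs on a single value, absolute or as a multiple of the upper limit of normal, and a baseline sample can meet them. Hematocrit is the exception, because it also requires a drop of at least 3 percentage points from baseline.

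**The concern.** The numerator can contain only subjects who start without the abnormality. The denominator also contains subjects who start with it. For them a new abnormality on that criterion is impossible by definition, so they lower the percentage without adding information about risk. The error has one direction: the printed percentage equals the incidence among subjects at risk, or falls below it.

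Laboratory safety is among the primary endpoints (SAP 3.2.1), and this table is where the SAP applies its own PCSV criteria to it. A reader will naturally take the percentage as the incidence of new significant abnormalities. Since the share already abnormal can differ from one criterion to the next, the dilution can differ too, and percentages in the same table would not be comparable with each other.

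**Working it through.** The plan states no PCSV rate, so there is no figure of its own to reproduce. The check is direct arithmetic.

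**Inputs**

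- N, subjects with a baseline and a post-baseline value: 140. This is the approximate planned enrollment (SAP 4.2, Protocol 17.1), with the assumption that every subject has both values.
- x, subjects who shift: 14 or 7, chosen for illustration.
- B, subjects PCSV at baseline, and b = B/N. The documents do not give b for any criterion, so a range is shown.

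**Formulas**

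- Percentage under SAP 9.3.3: x / N
- Incidence among subjects at risk: x / (N - B)
- Ratio of the first to the second: (N - B) / N = 1 - b

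The relative shortfall is therefore b itself, whatever the value of x.

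**Results for N = 140**

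| b | B | At risk, N - B | SAP, x = 14 | At risk, x = 14 | SAP, x = 7 | At risk, x = 7 |
|---|---|---|---|---|---|---|
| 0% | 0 | 140 | 10.0% | 10.0% | 5.0% | 5.0% |
| 2% | 3 | 137 | 10.0% | 10.2% | 5.0% | 5.1% |
| 5% | 7 | 133 | 10.0% | 10.5% | 5.0% | 5.3% |
| 10% | 14 | 126 | 10.0% | 11.1% | 5.0% | 5.6% |
| 20% | 28 | 112 | 10.0% | 12.5% | 5.0% | 6.3% |
| 30% | 42 | 98 | 10.0% | 14.3% | 5.0% | 7.1% |

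(At b = 2%, B is 2.8 rounded to 3.)

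For 14 shifts the gap is 0.2 points at b = 2%, 0.5 at 5%, 1.1 at 10%, 2.5 at 20% and 4.3 at 30%.

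**Where b can exceed zero.** For hematocrit b is zero, because no value can have fallen from itself. For criteria that are plain cut-offs, such as CK at 3 times the upper limit of normal or more, b can be positive, and the entry criteria set no laboratory limit that would prevent it. The SAP Preface describes a disease dominated by muscle atrophy and weakness. That makes CK a natural place to look, but the documents do not say how often CK is raised in these subjects.

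**The case against.** The strongest reply is that dividing by all subjects with paired values is a common shift-table convention, and that the SAP states it openly. The number of shifting subjects appears next to the percentage and does not depend on the denominator. All laboratory data are listed (SAP 9.3.3), and clinically significant abnormalities are also recorded as adverse events (Protocol 15.5). The study has one arm and no hypothesis test (SAP 7.2), so no decision rule uses this percentage. With b at 2% to 5%, a 10% rate moves by only 0.2 to 0.5 points.

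Most of this stands, and it limits the weight of the point. It does not remove it. The convention is harmless when the table shows every baseline category, because the reader can then recover the at-risk number. SAP 9.3.3 describes only the movement from non-PCSV to PCSV and does not commit to showing how many subjects were PCSV at baseline. Without that number the percentage can be corrected only from the subject listings.

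A reader might also infer two stronger claims, and the documents support neither.

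- **That Week 96 and early-termination values are lost from the numerator.** The shift is assessed over the treatment period, and Protocol 10.1.3 puts the Week 96 visit in a safety follow-up period that "will be conducted for subjects who complete the open-label treatment period". But SAP 9.3.2 counts Week 96 within the treatment period for the C-SSRS, SAP 10.3 lists it as a laboratory analysis visit, and SAP 9.3.3 runs its other laboratory summaries through Week 96. SAP 8.5 assigns early-termination assessments to the closest scheduled visit when that visit has no data. Taken together, the SAP text points to inclusion.
- **That this is the only laboratory result based on a threshold.** SAP 9.3.3 also plans shift tables by reference range, from baseline to each visit up to Week 96.

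**Conclusion.** The point holds in a limited form. As written, the percentage is (1 - b) times the incidence of new PCSV among subjects at risk. For 14 shifts in 140 subjects that means 10.0% printed against 10.5%, 11.1% or 12.5% at b = 5%, 10% or 20%. The identity is exact. The size rests on assumed values of b and on 140 subjects all having paired data.

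There is no effect for hematocrit, or for any other criterion that nobody meets at baseline. It would be wrong to conclude that new abnormalities go unreported: the count is right, and only the percentage can be too low when read as an incidence. This is a cheap improvement, not an error that threatens the safety conclusions.

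**What to change.** Replace the last sentence of SAP 9.3.3 with wording such as: For each criterion, the percentage is the number of subjects who were non-PCSV at baseline and meet the criterion after baseline, divided by the number who were non-PCSV at baseline and have at least one post-baseline value. Add a row for each criterion with the number of subjects PCSV at baseline.

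The cost is a change of SAP wording and of the denominator in one table, with no new data. The drawback is that denominators will differ between criteria, so each must be printed beside its percentage. Where nobody is PCSV at baseline, the percentage stays as it is.

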9.3.4. Vital Signs

Vital sign measurements and their change from baseline will be listed and summarized using descriptive statistics by visit up to week 96. Those parameters will include: heart rate (HR), supine and standing blood pressure (BP) (both systolic and diastolic), body temperature and weight. Furthermore, supine minus standing blood pressure (both systolic and diastolic) and their change from baseline will be summarized with descriptive statistics by visit. The body weight values and change from baseline to each post baseline visit up to week 96 will be plotted by visit.

The number and percentage of subjects with orthostatic hypotension as defined in section 8.4.3.5 will be tabulated by visit.

9.3.5. 12-Lead ECGs

All ECGs parameters will be listed and analyzed.

The ECGs will be assessed by the investigator and deemed “Normal”, “Abnormal, not clinically significant” (Abnormal, NCS) and “Abnormal, clinically significant” (Abnormal, CS) and tabulated by visit up to week 96 using frequency counts and percentages.

In addition, the numerical ECG parameters and their change from baseline generated by the central ECG laboratory (see section 8.4.3.4) will be summarized by descriptive statistics for each parameter by visit.

9.3.6. Physical Examinations

Physical examination including reason not done will be listed.

9.4. Subgroup analysis

The subgroup analysis will be performed for the following section.

- Section 9.1.1 Subject disposition stratified by region.
- Section 9.2.1.1 Change from baseline up to Week 96 in ALSFRS-R stratified by region.
- Section 9.2.1.2 Time to death, tracheostomy, or permanent assisted mechanical ventilation stratified by region.
- Section 9.3.1 TEAEs by SOC and PT stratified by region.

10. DATA PRESENTATION CONVENTIONS**10.1. Number of Digits to Report**

| Statistic | Specification | Apply to |
|--|---|---------------------------------|
| Minimum, Maximum | Same number of DPs as the data captured in the datasets | All original (i.e. non-derived) |
| | see section 8.4 | All derived data |
| Mean, Median, SD, SE, Confidence intervals | One more DP than used for Min Max | All |
| Percentages ^{*1} | 1 DP | All |
| Ratios | 3 DPs | All |
| p-values ^{*2} | 3 DPs | All |

*1 Percentages: use 1 place after the decimal point, except for the following cases:

If the percentage is equal to 0, then use "(0)" without a decimal

If the percentage is equal to 100, then use "(100)" without a decimal

*2 p-values: use 3 places beyond the decimal point, except for the following cases:

If the p-value is less than 0.001, then use p<0.001

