#### **10.1.2 End of Treatment**

The EOT visit will occur at Week 94, when the drug is commercially available in that country, or in the event the Sponsor discontinues the study.

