### **15.6 Recording and Reporting of Adverse Events**

All AEs, regardless of the relationship to IMP, occurring from the time written ICF will be obtained from a subject until the end of the safety Follow-up Period or the withdrawal of the subject from the study will be recorded.

NOTE: Elective hospitalization or procedure/surgery planned before subject enrollment for a preexisting medical condition does not constitute an AE unless the underlying disease or condition worsens after signing ICF.

All AEs will be recorded on an AE form in the eCRF. Reports should contain a description of the event, date of onset, date of resolution, severity, treatment required, relationship to IMP, action taken with the IMP, outcome and whether the event is classified as serious.

The Investigator will evaluate the severity of the AEs (as defined in Section 15.3) and will assess the causality between the AEs and the IMP (as defined in Section 15.4).

Pre-existing illnesses, which started prior to entry and are still ongoing at the start of the study, will not be considered AEs unless they worsen during the treatment period. Pre-existing conditions will be recorded as medical history.

If the Investigator becomes aware of any new safety information, or any safety information, which appears to be either study or IMP, related after the Final Follow-up period, then they must notify the Sponsor immediately.

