3. STUDY OBJECTIVE AND ENDPOINTS

3.1. Study Objectives

3.1.1. Primary Objective

To evaluate the long-term safety of oral edaravone at a dose of 105 mg administered once daily for 10 days out of a 14-day period, followed by a 14-day drug-free period for 96 weeks of treatment or until the drug is commercially available in that country.

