8.4.1.2. Demographic and Other Baseline Characteristics

8.4.1.2.1. Demographics:

Continuous: age, height, weight, Body Mass Index (BMI);

Categorical: age categorized as < 65 years versus \geq 65 years, and \leq 19, 20–29, 30–39, 40–49, 50–59, 60–69, \geq 70, gender, race, country and region defined as North America- NA, Western Europe -WE and Japan - JP

- BMI will be calculated as weight at A03 Baseline (kg) / {height at A01 Screening (m)}² and reported to 1dp.

Table 3: Demographic and Baseline Characteristics¹

| Category | Item | Type of Data | Definition/Breakdown |
|------------|------------------|--------------|--|
| Demography | Gender | Binary | Male, Female |
| | Race | Categorized | 
 1. White 2. Black or African American 3. Asian – Japanese 4. Asian - Not Japanese 5. American Indian or Alaska Native 6. Native Hawaiian or Pacific Islander 7. Not Reported 8. Other |
| | Age (year) | Continuous | |
| | | Categorized | ≤ 19, 20–29, 30–39, 40–49, 50–59, 60–69, ≥ 70 |
| | | Binary | <65, ≥ 65 |
| | Height (cm) | Continuous | |
| | Body weight (kg) | Continuous | |
| | BMI | Continuous | |
| | Country | Categorized | United States, Canada, Germany, France, Italy, Japan |
| | Region | Categorized | 
 1. North America-NA (United States and Canada) 2. Western Europe -WE (Germany, France and Italy) 3. Japan - JP |
| | Ethnicity | Categorized | 
 1. Hispanic or Latino 2. Not Hispanic or Latino 3. Not Reported 4. Unknown |

¹ Baseline characteristics not collected in MT-1186-A03 will be taken from MT-1186-A01

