9.3.1. Adverse Events

AEs that occurred on or after the first dose in the MT-1186-A03 will be summarized, which implies AE that occurred during MT-1186-A01 will not be summarized.

The following summaries will be provided:

- A Summary table of the overall incidence (number and percentage) and the number of events will be provided for TEAE, TEAE related to study drug, severe TEAEs, TESAEs, TEAEs leading to study treatment discontinuation and TEAEs leading to death.

The numbers and proportions of subjects will be calculated for the following:

- TEAEs by SOC and PT
- TEAEs by SOC, PT and severity
- Most Common ($\geq 5\%$ of patients) TEAEs by SOC and PT
- TEAEs related to study drug by SOC and PT
- TEAEs related to study drug by SOC, PT and severity
- TESAEs by SOC and PT
- TESAEs related to study drug by SOC and PT
- Severe TEAEs by SOC and PT
- Severe TEAEs related to study drug by SOC and PT
- TEAEs leading to study treatment discontinuation by SOC and PT
- TEAEs by SOC, PT and relationship to study drug
- TESAEs by SOC, PT and relationship to study drug
- TEAEs leading to death by SOC and PT

For these tables, SOC will be sorted by International Agreed Order; then within SOC, PT will be sorted by PT code.

The following summaries will be provided:

- A Summary table of the overall incidence (number and percentage) will be provided for Peripheral Neuropathy Standardized MedDRA query (SMQ) TEAEs

The numbers and proportions of subjects will be calculated for the following:

- TEAEs of Peripheral Neuropathy SMQ by SOC and PT
- Serious TEAEs of Peripheral Neuropathy SMQ by SOC and PT

TEAEs by Oral/PEG subgroup, SOC and PT

The numbers and proportions of subjects with TEAEs and event rate of TEAEs will be calculated by Oral/PEG subgroup, SOC and PT. The event rate of TEAEs will be calculated as the number of TEAEs divided by total exposure to investigational product by Oral/PEG dosing and expressed as 100 person years. Any TEAE occurred after subject switched to PEG will be classified under the PEG subgroup.

The exposure (in days) under Oral in cycle switched to PEG will be calculated as difference: Oral days=PEG switch Date during MT-1186-A01 or MT-1186-A03 - Cycle first date. If Oral days is less than 0 then Oral days will be 0.

The oral days does not exceed actual exposure duration (days) in the cycle. The exposure under PEG will be calculated as difference:

PEG days= actual exposure duration - Oral days.

TEAEs by Cycle

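### TEAEs by region are planned only as crude percentages, although follow-up can end early when the drug becomes available in a country, so unequal follow-up may be misread as a regional difference in risk

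*SAP*

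**What the plan says.** **Length of treatment and follow-up.** The primary objective (SAP 3.1.1) covers treatment "for 96 weeks of treatment or until the drug is commercially available in that country". Protocol 10.1.2 makes the same event a trigger for the end-of-treatment visit: "The EOT visit will occur at Week 94, when the drug is commercially available in that country". Under Protocol 15.6, adverse events occurring "until the end of the safety Follow-up Period or the withdrawal of the subject from the study will be recorded", so collection stops shortly after treatment does.

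**Region.** SAP Table 3 lists the countries as "United States, Canada, Germany, France, Italy, Japan" and groups them into North America, Western Europe and Japan.

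**TEAE tables.** SAP 9.4 includes "Section 9.3.1 TEAEs by SOC and PT stratified by region". The statistic comes from SAP 9.3.1: "The numbers and proportions of subjects will be calculated for the following". The denominator comes from SAP 7.1: "The denominator for the percentages will be the total number of subjects in the treatment group and analysis population being presented, unless otherwise specified".

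**Time-based safety summaries elsewhere.** SAP 9.3.1 plans one TEAE rate, for the Oral/PEG subgroups: "The event rate of TEAEs will be calculated as the number of TEAEs divided by total exposure to investigational product by Oral/PEG dosing". It also plans TEAEs by cycle group (1-6, 7-12, 13-18, 19-24), and SAP 9.1.6 plans exposure by cycle, in total and in person-years. Neither the cycle-group table nor the exposure summary is among the analyses that SAP 9.4 stratifies by region.

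**The concern.** Region is built from country, and country can determine how long a subject is treated and observed. A percentage of subjects with at least one event rises with observation time. Two regions with the same underlying risk would therefore show different percentages if one left the study earlier because the drug reached its market.

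The other two outcome analyses that SAP 9.4 lists by region make some allowance for unequal follow-up: the time-to-event endpoint uses Kaplan-Meier with censoring, and ALSFRS-R uses a repeated-measures model on observed visits. The TEAE table makes none, although safety is the primary objective and TEAEs are a primary endpoint. At stake is how a reader interprets the regional safety table: a lower percentage may be taken as better tolerability or as under-reporting when it only reflects less time at risk.

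**Working it through.** The plan gives no regional rate, regional follow-up or availability date, and the sample size of about 140 is not derived from a formula. There is no figure of the plan to reproduce; what follows is an illustration.

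**Inputs from the documents.** 24 cycles of 28 days = 672 days = 96 weeks; 672/365.25 = 1.840 years. 10 planned dosing days per cycle × 24 = 240 days (SAP 8.4.1.4).

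**Assumed inputs.** The same first-event rate h in both regions, with one region stopping at 48 weeks (336 days, 0.920 years) or 72 weeks (504 days, 1.380 years) and the other followed to 96 weeks.

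**Step 1: constant hazard, no dropout.** Crude incidence p(t) = 1 − exp(−h·t). For h = 0.2 per year:
- 48 weeks: 1 − exp(−0.2 × 0.920) = 16.8%
- 96 weeks: 1 − exp(−0.2 × 1.840) = 30.8%

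| h per year | 48 weeks | 96 weeks | Ratio |
|---|---|---|---|
| 0.1 | 8.8% | 16.8% | 0.52 |
| 0.2 | 16.8% | 30.8% | 0.55 |
| 0.4 | 30.8% | 52.1% | 0.59 |

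With 72 against 96 weeks and h = 0.2, the figures are 24.1% and 30.8% (ratio 0.78). With equal follow-up the ratio is 1.

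**Step 2: attrition.** With a dropout hazard d in both regions, p(t) = h/(h + d) × [1 − exp(−(h + d)·t)]. For h = 0.2 and an assumed d = 0.36 per year:
- 48 weeks: 0.357 × [1 − exp(−0.56 × 0.920)] = 14.4%
- 96 weeks: 0.357 × [1 − exp(−0.56 × 1.840)] = 23.0%

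The ratio is 0.63.

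**Step 3: front-loaded hazard.** Assume 20% incidence at 96 weeks, so the cumulative hazard is −ln(0.8) = 0.223. Let half of it fall in the first 24 weeks and the rest evenly over the remaining 72. By week 48 the share is 0.5 + 0.5/3 = 0.667, so p = 1 − exp(−0.667 × 0.223) = 13.8% against 20.0%, a ratio of 0.69. A constant hazard with the same 96-week incidence gives 10.6% against 20.0%, a ratio of 0.53.

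**Step 4: does a rate remove the artefact?** Expected person-years to first event or end of follow-up are [1 − exp(−h·t)]/h per subject. In the h = 0.2 case of Step 1 this is 0.168/0.2 = 0.840 and 0.308/0.2 = 1.54 years. The rates are 0.168/0.840 and 0.308/1.54, that is 20 per 100 person-years in both regions. Under the front-loaded hazard of Step 3 the average hazards differ: 0.149/0.920 = 0.162 per year at 48 weeks and 0.223/1.840 = 0.121 at 96 weeks. A single rate would then overcorrect, which is why a table by period is also needed.

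**Step 5: which person-time?** SAP 8.4.1.4 counts dosing days. Over 24 planned cycles that is 240/365.25 = 0.66 years per subject, against 1.84 calendar years. A rate on that denominator would be 672/240 = 2.8 times the calendar-time rate.

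**The case against.** The strongest reply is that this is an exploratory, descriptive table. SAP 7.2 plans no hypothesis tests, SAP 9.4 says stratified rather than compared, and no regional safety conclusion is planned. That stands: there is no error rate to protect, and the risk is misreading.

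A reader might infer that regions with earlier availability will look safer. The documents do not support that certainty. They give no availability dates and no follow-up by region. Availability is also set by country, so countries within North America or Western Europe may stop at different times and a region need not have one cut-off.

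A reader might also infer that nothing in the plan reveals unequal follow-up. That is too strong. SAP 9.4 gives disposition by region, with discontinuations and reasons. ALSFRS-R is also stratified by region, and the number of observations at Weeks 24, 48, 72 and 96 should show roughly how many subjects remained. Listings of exposure and TEAEs are planned. These would expose a much shorter region, but they do not give time at risk. Nor does the SAP say whether a subject who stops at commercial availability counts as a completer.

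A third tempting reading is that the overall TEAE percentages are undermined in the same way. For the whole population, however, the plan already has TEAEs by cycle group, exposure by cycle and total person-years, so the timing of events and the fall in exposure are at least partly visible. The gap is specific to the regional presentation.

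Finally, a rate per person-year assumes a roughly constant hazard, which is doubtful in a progressive disease, and with about 140 subjects in three regions most intervals for individual terms will be wide. Both points are fair and shape the fix.

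**Conclusion.** The point holds as a presentation gap. The protocol allows treatment and adverse event follow-up to end at a country-level event, region is a grouping of countries, and the only planned regional TEAE statistic takes no account of time at risk. If follow-up differs between regions, the percentages may differ with equal underlying risk, and the bias lowers the figure for the region followed for less time.

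Its size cannot be determined from the documents. The ratios of 0.52 to 0.59 assume 48 against 96 weeks, constant hazard and no dropout. The attrition and front-loaded examples give 0.63 and 0.69, and 72 against 96 weeks at 0.2 per year gives 0.78. These are illustrations of direction and possible scale, not predictions. The issue deserves correction because the extra information is inexpensive, not because a biased regional conclusion is certain.

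**What to change.** In SAP 9.4, add by region:

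1. Duration of follow-up and calendar person-years, from first A03 dose to end of adverse event collection.
2. Beside the crude percentages, which stay, the number of subjects with a first event per 100 person-years at risk with exact 95% CI. Time at risk is calendar time from first A03 dose to first event or end of adverse event collection. Give this at least for any TEAE, serious TEAEs and the most common preferred terms (≥5% of patients, a list SAP 9.3.1 already plans).
3. The existing cycle-group TEAE table, with subjects at risk in each cycle group as the denominator. This shows whether a difference persists within the same period of follow-up and does not rest on a constant hazard.

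State that the exposure of SAP 8.4.1.4 is not the denominator for these rates.

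The cost is SAP wording, extra tables and a new derivation. The Oral/PEG calculation cannot simply be reused, because it divides the number of events by dosing-day exposure, while this rate needs first events and calendar time censored separately for each event category. Intervals will be wide for the less frequent terms, which is the reason for limiting the rates to the categories above. No new data, visits or protocol change are needed, and SAP Section 2 allows updates before final database lock.
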